All patients who withdraw from the treatment period or who complete the total 52-week treatment period must return for post-*Week 52* SFU assessments at 12, 24, 36, and 48 weeks after either the early withdrawal visit or study treatment completion, respectively. Thus, patients will be followed for approximately 1 year in the SFU period. A schedule of assessments during the SFU period is provided in [Appendix 2](#).

Before Week 12, patients who experience treatment failure (as defined in Section [3.1.3](#)) will require an early withdrawal visit and will be followed in the SFU period to receive standard-of-care treatment per the investigator's best medical judgment.

From Week 12 through Week 52, patients who experience treatment failure (as defined in Section [3.1.3](#)) are eligible to receive rescue therapy during the treatment period with another immunosuppressive medication, IV Ig, plasmapheresis, or another treatment or procedure as per the investigator's best medical judgment. An early withdrawal visit is not required for a patient to receive rescue therapy, and patients should continue to be followed in the study per the 52-week treatment period (see [Appendix 1](#)).

If a patient receives rescue therapy with rituximab, the number and timing of infusions will be at the discretion of the investigator. Every effort will be made to maintain the study blind, but the patient may be unblinded at the discretion of the Principal Investigator's safety assessment. Patients who receive rescue infusions with rituximab from Week 12 through Week 24 will not receive the scheduled rituximab or matching placebo infusions on Days 168 and 182. Careful consideration should also be given as to whether MMF/matching placebo are continued following rescue therapy with any immunosuppressive medication.

Evaluation of the primary endpoint will occur at Week 52. To prevent potential unblinding due to observed efficacy or laboratory changes, a dual-assessor approach will be used to evaluate efficacy and safety.

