4.2 METHOD OF TREATMENT ASSIGNMENT AND BLINDING

A total of approximately 132 patients will be recruited into this study and will be randomized in a 1:1 ratio to two treatment arms using an interactive/web voice response system (IxRS). Patient randomization numbers will be generated by the IxRS vendor. A unique randomization number will be linked to the patient's identification number (electronic Case Report Form [eCRF] number) via the IxRS. Patients may not be dosed at any visit prior to receiving the IxRS-assigned medication numbers. Patients who enroll in this study and who have completed treatment as specified are not permitted to be re-randomized to this study; however, re-screening is allowed as described in Section 4.5.1.3.

Randomization will be stratified by duration of illness (newly diagnosed [diagnosed within 1 year prior to screening] vs. diagnosed greater than 1 year from screening) and geographical region (North America [U.S./Canada] vs. rest of world). Patients prematurely discontinued from the study will not be replaced.

The randomization list will not be available at the study center, to the Sponsor monitors, or the Sponsor's project team, including the project statisticians. The medication allocation will only be known to the unblinded drug accountability monitors and an unblinded on-site pharmacist who will prepare locally sourced methylprednisolone for patients receiving rituximab and a saline solution for patients receiving rituximab placebo, to be administered prior to the infusion.

Every effort will be made to maintain the blind; for example, opaque infusion bags and IV lines will be used if local methylprednisolone has noticeable coloring compared with the saline solution. To maintain the blind, investigational sites will not receive data related to CD19+ B-cell counts, PK results, or HACA results. CD19+ B-cell counts will be made available to the investigator at the end of SFU period. In addition, to prevent potential unblinding, there will be an efficacy assessor and a safety assessor for observed efficacy and safety evaluations. Only the safety assessor will have access to adverse event reports and laboratory test results, and will determine dose adjustments and treatment decisions.

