4.4.2 Additional Permitted Therapy and Procedures

Patients who use oral contraceptives, hormone-replacement therapy, or other maintenance therapy should continue their use.

Patients not already taking vitamin D (400 IU/day) and calcium supplements (1200 mg/day calcium citrate or 1500 mg/day calcium carbonate) may start these supplements at study initiation. *Pneumocystis jirovecii* pneumonia prophylaxis may be performed according to local clinical practice guidelines and investigator judgment.

From Week 12 through Week 52, an additional provision is made for patients who would otherwise be withdrawn from the study because of lack of efficacy. Specifically, patients who experience treatment failure between Week 12 through Week 52 are eligible to receive rescue therapy with another immunosuppressive medication, IV Ig, plasmapheresis, rituximab, or another treatment or procedure as per the investigator's best medical judgment and continue to be followed in the 52-week treatment period per the treatment period schedule of assessments (see [Appendix 1](#)). Details of additional therapies for PV should be reported as concomitant medications.

If a patient receives rescue therapy with any medication, dose and dosing schedule will be at the discretion of the investigator. Every effort will be made to maintain the study blind, but the patient may be unblinded at the discretion of the Principal Investigator's safety assessment. Patients who receive rescue infusions with rituximab from Week 12 through Week 24 will not receive the scheduled rituximab or matching placebo infusions on Days 168 and 182. Careful consideration should also be given as to whether MMF/matching placebo are continued following rescue therapy with any immunosuppressive medication.

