4.5 STUDY ASSESSMENTS

To prevent potential unblinding due to observed efficacy or changes in laboratory test results, a dual-assessor approach will be used to evaluate efficacy and safety. The efficacy assessor should be a dermatologist or skilled physician PV assessor. To ensure consistency, wherever possible it is required that the same efficacy assessor continues to assess all efficacy parameters throughout the study for any particular patient. The efficacy assessor will have access only to the efficacy data. The safety assessor should be a dermatologist. The safety assessor will have access to both safety and efficacy data and will make all treatment decisions based on the patient's clinical response and laboratory test results.

It is essential that assessments by the patient (e.g., patient-reported outcomes [PROs]) and efficacy assessor are made before those of the safety assessor. Consequently, assessments should be made in the following order:

1. Patient-reported outcomes: DLQI, PGIC, EQ-5D-3L, and Skindex-29
2. Clinician-reported outcome (efficacy assessor): CGIC
3. Efficacy assessor: PDAI (activity scale), lesion count, flare assessment
4. Safety assessor: adverse event and laboratory assessments, corticosteroid dose assessment, and all treatment decisions

Please see [Appendix 1](#) for the schedule of assessments performed during the study.

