4.6.4 Dose Modification and Treatment Interruption

In the event that the patient develops a medically significant NCI CTCAE Grade 3 or 4 infection, no further doses of rituximab/placebo or MMF/placebo study drug treatment should be provided until the infection has resolved.

Rituximab and matching placebo: Prolonged B-cell depletion is the expected outcome of rituximab treatment and is not considered a toxicity.

Patients who experience a Grade 4 (life-threatening) event during an infusion of rituximab (or matching placebo) should have their infusion stopped. Additional infusions of rituximab (or matching placebo) should not be given.

MMF and matching placebo: During the 52-week treatment period, the MMF (or matching placebo) dose should remain as stable as possible. If reductions in dose are necessary because of tolerability, decreases will be allowed in 500-mg decrements and must be recorded on the appropriate eCRF. If neutropenia develops ($ANC < 1.3 \times 10^3/\mu L$), dosing with MMF (or matching placebo) should be interrupted or the dose should be reduced.

Guidelines for dosage modification and treatment interruption or discontinuation of MMF are provided in the MMF prescribing information.

Rituximab—F. Hoffmann-La Roche Ltd
59/Protocol WA29330, Version 5

In addition to the above, the following safety criteria must be met prior to resuming either rituximab/placebo or MMF/placebo study drug treatment:

- ANC $\geq 1.3 \times 10^3/\mu\text{L}$ at the last blood sample analysis
- The patient has not developed any of the following:
 - Primary or secondary immunodeficiency, including HIV infection
 - Known active infection of any kind (excluding fungal infections of nail beds), or any major episode of infection requiring hospitalization or treatment with IV anti-infectives within 4 weeks prior to infusion or within 2 weeks prior to oral MMF (matching placebo) and completion of oral anti-infectives within 2 weeks prior to infusion or within 1 week prior to oral MMF (matching placebo)
 - The patient has not developed any conditions that, in the investigator's opinion, would preclude the patient from receiving further courses of treatment, such as: any new or uncontrolled disease including, but not limited to, cardiovascular disease; nervous system, pulmonary, renal, hepatic, endocrine, or gastrointestinal disorders; or malignancies
- Patient is not pregnant or breastfeeding

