Appendix 1 Schedule of Assessments (cont.)

completion of rituximab or rituximab placebo infusion, respectively.

- ^u Samples to be collected prior to administration of IV methylprednisolone or saline solution for patients in the rituximab or rituximab placebo arms, respectively.
- ^v The optional DNA sample can be collected prior to or after study drug administration.
- ^w Methylprednisolone or saline solution should be administered by slow IV infusion to be completed at least 30 minutes prior to each infusion of rituximab or rituximab placebo, respectively.
- ^x Rituximab at a dose of 1000 mg (or matching placebo) will be administered by IV infusion on Day 1 and Day 15, with repeat rituximab (or matching placebo) administration on Day 168 and Day 182 provided specific safety criteria have been met (see Section 4.6.4). See [Appendix 3](#) for administration instructions.
- ^y Administration of the first dose of study treatment (Day 1) should occur within 24 hours following the baseline assessments; however, administration up to 72 hours will be allowed when necessary. The second infusion should occur on Day 15 ± 1 day.
- ^z MMF (500 mg or matching placebo) will be administered orally twice daily (Q12H) starting on Day 1. Patients will be initiated on MMF at 1 g/day or matching placebo in divided oral doses (Q12H). The MMF dose will be titrated to achieve a goal of 2 g/day in divided oral doses (1 g Q12H) by Week 2.

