Appendix 11 Telemedicine (cont.)

INFUSION DAYS 1 (WEEK 1), 15 (WEEK 2), 168 (WEEK 24), AND 182 (WEEK 26)

All patients, regardless of state of residence, will receive their infusions and associated study visit assessments at the TM PI site.

- Infusions: Rituximab (and matching placebo) should be administered in a hospital, clinic, or healthcare-related environment where full resuscitation facilities are immediately available and under the close supervision of an experienced healthcare professional.
- All infusion reactions and adverse events will be documented and communicated immediately, as appropriate, to the TM safety assessor and the Sponsor as per the protocol.
- Infusion day laboratory assessments:
 - All laboratory assessments scheduled for infusion days should be performed as described in the schedule of assessments (see [Appendix 1](#)). Blood draws that are timed to occur before and after the first infusions will be performed at the infusion center.

ALL OTHER STUDY VISITS

Weeks 4–20 and 32–52, Withdrawal, and Safety Follow-Up (Weeks 12, 24, 36, and 48 after Withdrawal or Completion of Treatment)

For all patients, regardless of state of residence, these study visits will be conducted by a MRN at the patient's home.

- TM research coordinator coordinates with MRN to schedule visits to the patient's home

Assessments specified for evaluation days other than infusion days should be performed within 3 days of the scheduled visit.

The MRN will visit the patient's home on each evaluation day noted in the schedule of assessments (see [Appendix 1](#) and [Appendix 2](#)). Assessments and procedures, including laboratory assessments and recording of adverse events and concomitant medications will be performed by the MRN. Results will be made available to the safety assessor via the TM application.

For assessments of disease activity:

- Disease activity will be assessed by the patient using the Patient Global Impression of Change (PGIC). The patient will complete the patient-reported outcome (PRO) questionnaires (Dermatology Life Quality Index [DLQI], European Quality of Life

Rituximab—F. Hoffmann-La Roche Ltd
134/Protocol WA29330, Version 5

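### The rule cancelling scheduled infusions after rituximab rescue ends at Week 24, but the last scheduled infusion is at Week 26, so no rescue-linked rule covers the days between

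*Protocol*

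**What the plan says.** The cancellation rule appears in Protocol 3.1.1 and again in 4.4.2: "Patients who receive rescue infusions with rituximab from Week 12 through Week 24 will not receive the scheduled rituximab" or placebo infusions on Days 168 and 182. Neither place carries it beyond Week 24.

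The period in which rescue is allowed is longer. Section 4.4.2 says that "patients who experience treatment failure between Week 12 through Week 52 are eligible to receive rescue therapy" and names rituximab among the options. Section 3.1.1 adds: "If a patient receives rescue therapy with rituximab, the number and timing of infusions will be at the discretion of the investigator".

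The last scheduled infusion falls after the rule has ended. Appendix 11 labels the infusion visits as "INFUSION DAYS 1 (WEEK 1), 15 (WEEK 2), 168 (WEEK 24), AND 182 (WEEK 26", and the schedule in Appendix 1 gives Day 168 ±3 and Day 182 ±1. Appendix 1 footnote x provides for treatment "with repeat rituximab (or matching placebo) administration on Day 168 and Day 182 provided specific safety criteria have been met", pointing to Section 4.6.4.

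Treatment decisions belong to the safety assessor. Section 4.2 says this assessor sees adverse event and laboratory reports "and will determine dose adjustments and treatment decisions". Section 4.5 says: "The safety assessor will have access to both safety and efficacy data and will make all treatment decisions".

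**The concern.** The rule protects the Day 182 infusion from following closely on rescue rituximab, but it stops about two weeks before that infusion. Rescue at Week 24 cancels Day 182. Rescue a week later, nearer to Day 182, does not. Nothing in the protocol explains why the closer rescue should have the weaker rule, so this reads as a boundary set at the wrong week.

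What is at stake is dosing safety in the rituximab arm. Such a patient could receive the Day 168 dose, rescue rituximab and a further 1,000 mg on Day 182 within about two weeks. In the MMF arm the Day 182 infusion is placebo, so it adds no exposure. Judgment is also a weaker safeguard here than usual. Under Section 4.2 sites receive no CD19+ or PK results, so unless the patient is unblinded the assessor cannot know whether the Day 168 infusion was active or whether the Day 182 infusion will be.

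**Working it through.** **Week labels.** 24 × 7 = 168 and 26 × 7 = 182, so the protocol's labels (Day 168 = Week 24, Day 182 = Week 26) reproduce.

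**Length of the gap.** Days uncovered = infusion day − last day covered by the rule − 1. The infusion falls on Day 181, 182 or 183. The last covered day depends on how Week 24 is read.

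| Last covered day | Infusion Day 181 | Day 182 | Day 183 |
|---|---|---|---|
| Day 165 (Week 24 visit three days early) | 15 | 16 | 17 |
| Day 168 (nominal) | 12 | 13 | 14 |
| Day 171 (end of visit window) | 9 | 10 | 11 |
| Day 174 (calendar week from Day 168) | 6 | 7 | 8 |

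The nominal gap is 13 days (Days 169 to 181), the range is 6 to 17 days, and no reading gives zero. Section 5.1.1.9 lets the second infusion of a course be delayed for a new infection up to 28 days from the first. In the second course that is 168 + 28 = Day 196, leaving Days 169 to 195, or 27 days, for those patients.

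**Does another rule close it?**
- Section 4.6.2 (mandatory discontinuation) lists pregnancy, PML, malignancy, SJS/TEN, severe allergic reaction, Grade 4 infusion events and pure red cell aplasia. Rescue is not on the list.
- Section 4.6.4 requires adequate ANC, no active or recent major infection, no immunodeficiency, and no pregnancy or breastfeeding. Rescue triggers none of these. It also has an investigator-opinion clause on conditions that "would preclude the patient from receiving further courses of treatment", which does not name rescue rituximab.
- Section 5.1.1.9 delays an infusion for infection, not for rescue.
- Section 4.4.3 asks for caution with immunosuppressants alongside study drug. It does not bar them.
- The sentence in 3.1.1 about reconsidering study drug after rescue concerns MMF or its placebo only.

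**Expected number.** The rescue period, Day 84 to Day 364 inclusive, is 364 − 84 + 1 = 281 days. The rituximab arm has about 132 / 2 = 66 patients. The documents give no rescue rate, so assume that 5% to 20% receive rituximab rescue, evenly over the 281 days. Expected patients = 66 × rate × gap / 281.
- Nominal gap, 13 days: 66 × 0.05 × 13 / 281 = 0.15 to 66 × 0.20 × 13 / 281 = 0.61.
- Extremes: 66 × 0.05 × 6 / 281 = 0.07 to 66 × 0.20 × 17 / 281 = 0.80.
- Rate needed for one expected patient at the nominal gap: 281 / (66 × 13) = 33%.

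The 27-day gap is left out because it applies only to patients whose infusion is delayed for infection.

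**Dose.** Rescue dosing is discretionary. Assuming one 1,000 mg rescue infusion, Day 168 + rescue + Day 182 = 3 g, against 2 g scheduled and about 2.8 g for the 4 × 375 mg/m² cycle described in Section 3.3.1. More rescue infusions would raise the total.

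**The case against.** Rescue with rituximab is a deliberate act by a team that knows the schedule. The safety assessor controls treatment decisions, study treatment can be stopped at any time (3.1.1), unblinding is available, and Section 4.4.3 urges caution. Stacking by oversight is therefore unlikely, and leaving a rare overlap to the physician fits how the protocol handles rescue generally. This stands as a reason for a low rating. It does not explain why the sponsor wrote a fixed rule up to Week 24 and none for the two weeks after.

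The harm is also unproven. Section 5.3.5.12 says there are no safety data on rituximab overdose, which does not show that 3 g is dangerous. The assumed 3 g is about 7% above the 2.8 g cycle (3.0 / 2.8 = 1.07). Appendix 10 lists one patient given 7 × 375 mg/m², about 4.9 g at the same rate (2.8 / 4 × 7). That is weak evidence, but the point that harm is unquantified stands.

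The repair does not remove all stacking. Day 168, Day 182 and a rescue dose on Day 183 still make 3 g in 16 days. This stands too. The repair corrects the boundary of an existing rule and does not cap rescue dosing.

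A reader might infer that judgment alone can stop the Day 182 infusion. The documents do not support that, because the mandatory criteria in 4.6.2, 4.6.4 and 5.1.1.9 still apply to a rescued patient. What is missing is a rule triggered by the rescue itself.

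**Conclusion.** The point holds as a minor dosing-safety correction. The cancellation rule ends at Week 24, the last scheduled infusion is at Week 26, and rituximab rescue is permitted in between. The gap is above zero on every reading of the visit windows. Its exact length is not fixed by the text, so no single figure should be quoted as established.

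Probably fewer than one patient would be affected. That rests on an assumed rescue rate and even timing. Even timing probably overstates the number, since an investigator who knows that Day 182 is due can wait or choose another rescue.

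A reader might also infer that the trial's results are at risk. They are not. Starting rescue is itself treatment failure, and SAP 4.7.1.4 excludes data from that point for the primary endpoint. SAP 4.9 cuts the main safety analysis at rescue, with selected post-rescue safety outputs summarized separately.

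**What to change.** In Protocol 3.1.1 and 4.4.2 replace the cancellation sentence with: *Once a patient has received rituximab as rescue, any scheduled rituximab or matching placebo infusion (Day 168 and/or Day 182) not yet given at the time of rescue will be omitted.* Repeat it in Appendix 1 footnote x.

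Wording by infusions not yet given, rather than by week number, closes the gap under every visit-window reading and when an infusion is delayed for infection. It applies equally to both arms.

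The cost is one sentence in two sections and one footnote. The downside is that a patient rescued between the two infusions does not complete the second blinded course. The sponsor already accepts this for rescue at Week 24 once Day 168 has been given. The change does not limit discretionary rescue rituximab soon after a study infusion.

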3.1.2 Corticosteroid Treatment

Patients eligible for this study will be receiving 60–120 mg/day background oral prednisone or equivalent (1.0–1.5 mg/kg/day) at study entry. During the screening period (up to 28 days), the daily corticosteroid dose may be tapered, as directed by the investigator on the basis of disease activity and tolerability to reach a dosage of 60 or 80 mg/day by Day 1. Thereafter, corticosteroid treatment should then be tapered according to the treatment guideline in [Table 1](#), which provides recommended doses based on the presence of disease activity, defined as the appearance of new lesions or the extension of established lesions. The decision to taper the corticosteroid dose can be affected by physician preferences, patient tolerability, and local practices, among

Rituximab—F. Hoffmann-La Roche Ltd
32/Protocol WA29330, Version 5

other considerations. The oral corticosteroid dose may be increased during the study as needed as the primary intervention for control of disease activity. Prednisone (or equivalent) will be sourced locally.

The goal of study treatment is to maintain disease control and ultimately achieve disease remission. Oral corticosteroids will be tapered to the target prednisone (or equivalent) dosage of 0 mg/day by Week 24 (or sooner, if appropriate). From Week 24 to Week 52, the corticosteroid dosage should be maintained at 0 mg/day. However, patients who experience a disease flare (as defined in Section 3.4.1.2) at 0 mg/day should restart at Step 5 of [Table 1](#) (20 mg/day). Patients whose disease is not controlled after increasing the corticosteroid dose up to an allowable maximum dose of 240 mg/day will be considered to have experienced treatment failure and may receive standard-of-care treatment per the investigator's best medical judgment. Use of minimal concomitant topical corticosteroids will be permitted at the investigator's discretion but will be tracked carefully during the course of the study.

Table 1 Corticosteroid Treatment Guideline

Step	No. of Weeks	Daily Dose of Prednisone or Equivalent	Presence of Disease Activity ^a	
			No	Yes
1 (start) ^b	1 week	80 mg	Go to Step 2	Go to Step A
A	1 week	120 mg	Go to Step 2	Go to Step B
B	1 week	240 mg	Go to Step A	Discontinue taper ^c
2 (start) ^b	1 week	60 mg	Go 1 step forward	Go to Step 1
3	1 week	40 mg		Go 1 step back
4	2 weeks	30 mg		Go 2 steps back
5	2 weeks	20 mg		
6	2 weeks	15 mg		
7	2 weeks	12.5 mg		
8	2 weeks	10 mg		
9	2 weeks	7.5 mg		
10	2 weeks	5 mg		
11	2 weeks	2.5 mg		
12	During complete remission	0 mg		Restart at Step 5

Notes: On Day 1, start the oral corticosteroid regimen with an initial dosage of 60 or 80 mg/day prednisone (or equivalent), as outlined in the schedule. Increase the dose if disease activity is present after 1 week. If necessary, increase the dose again (to 240 mg/day) if disease activity is still present after the second week.

^a Disease activity is defined as the appearance of new lesions or the extension of established lesions.

^b Patients on 80 mg/d on Day 1 will start at Step 1. Patients on 60 mg/d on Day 1 will start at Step 2.

^c Patients whose disease is not controlled after increasing the corticosteroid dose to 240 mg/day will be considered to have experienced treatment failure and may receive standard-of-care treatment per the investigator's best medical judgment.

Source: Modified from Mentink LF, Mackenzie MW, Tóth GG, et al. Randomized controlled trial of adjuvant oral dexamethasone pulse therapy in pemphigus vulgaris (PEMPULS Trial). *Arch Dermatol* 2006;142:570–6.

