3.1.3 Definition of Treatment Failure

Treatment failure is the occurrence of any one of the following events:

- After disease control has been achieved, a two-step increase in prednisone (or equivalent) dose to ≥ 20 mg/day for more than 2 weeks to treat increased disease activity during the corticosteroid taper
- Failure to achieve disease control after receiving 240 mg/day PO prednisone (or equivalent) for 1 week

Disease control is defined as the time at which new lesions cease to form and established lesions begin to heal (beginning of the consolidation phase).

- Increase in MMF/matching placebo dosage above 2 g/day
- Initiation of any rescue therapy (addition of another immunosuppressive medication, additional rituximab open-label doses, IV Ig, plasmapheresis, or another treatment or procedure) as determined by the investigator's best medical judgment

Patients experiencing treatment failure prior to achieving sustained complete remission will be categorized as non-responders in the primary analysis, but will continue to be followed in the study per the schedule of assessments. Patients who achieve sustained complete remission without experiencing an event constituting treatment failure beforehand will not be categorized as non-responders, regardless of whether they subsequently meet the criteria during the remaining treatment period.

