Appendix 1 Schedule of Assessments

Week	Screen (-28 to -1)	1	2	4	8	12	16	20	24	26	32	40	48	52	WD ^a	SFU ^b
		1 (BL and Rz)	15 ±1	28 ±3	56 ±3	84 ±3	112 ±3	140 ±3	168 ±3	182 ±1	224 ±3	280 ±3	336 ±3	364 ±3		
Informed consent	x															
Medical history, ^c previous medications, and baseline conditions	x															
Pregnancy test (serum) ^d	x															
Pregnancy test (urine) ^d		x		x	x	x	x	x	x	x	x	x	x	x		
Complete physical examination ^e	x															
Body weight	x								x					x	x	
Height	x															
Vital signs ^f	x	x ^g	x ^g						x ^g	x ^g				x	x	
ECG	x															
CXR ^h	x															
Efficacy and PRO/ClinRO																
Disease activity (PDAI)	x	x		x	x	x	x	x	x		x	x	x	x	x	x
Flare assessment	x	x	x	x	x	x	x	x	x	x	x	x	x	x	x	x

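### For a patient starting at 60 mg/day, the note under the corticosteroid table gives 240 mg/day after two active weeks where the table gives 120 mg/day, which moves the earliest 240 mg/day treatment failure from the end of Week 4 to the end of Week 3

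*Protocol*

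**What the plan says.** Protocol Section 3.1.2 introduces Table 1 as a guideline "which provides recommended doses based on the presence of disease activity". Footnote b sets the entry points: an 80 mg/day patient starts at Step 1, and "Patients on 60 mg/d on Day 1 will start at Step 2". When disease activity is present, Step 2 (60 mg) leads to Step 1 (80 mg), Step 1 to Step A (120 mg) and Step A to Step B (240 mg). Each of these steps lasts one week. Activity at Step B ends the taper, and footnote c treats lack of control there as treatment failure.

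The note under the table addresses both starting doses together. It calls for an increase after one active week, without naming the dose, and continues: "If necessary, increase the dose again (to 240 mg/day) if disease activity is still present after the second week". It makes no exception for the 60 mg/day start.

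Protocol Section 3.1.3 and SAP Section 4.2 list as treatment failure: "Failure to achieve disease control after receiving 240 mg/day PO prednisone (or equivalent) for 1 week". Under Protocol Section 3.1.1, patients who fail before Week 12 "will require an early withdrawal visit and will be followed in the SFU period to receive standard-of-care treatment". SAP Appendix 4 reproduces the table, the note and the footnotes, so it does not say which governs.

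**The concern.** One dosing guideline gives two answers for the same patient at the same visit, and the answers differ by a factor of two at the top of the permitted range, since 240 mg/day is the allowable maximum. A site that follows the note skips the 120 mg/day step.

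The step also feeds the endpoint rules. A week at 240 mg/day without control is treatment failure. Before Week 12 that means an early withdrawal visit, and a failure before sustained complete remission makes the patient a non-responder. Cumulative oral corticosteroid dose is the first-ranked secondary endpoint (SAP Section 4.7), and corticosteroid-related adverse events in relation to exposure are a safety objective. Two sites could therefore give different doses to identical patients, and one could declare failure a week before the other, with both following the protocol.

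**Working it through.** **Escalation paths with activity at every weekly check** (entry steps from footnote b; destinations from the disease-activity column of Table 1; note as quoted)

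| Start | Source | Week 1 | Week 2 | Week 3 | Week 4 | Earliest 240 mg/day failure |
|---|---|---|---|---|---|---|
| 80 mg | Table | 80 | 120 | 240 | – | end of Week 3 |
| 80 mg | Note | 80 | increased | 240 | – | end of Week 3 |
| 60 mg | Table | 60 | 80 | 120 | 240 | end of Week 4 |
| 60 mg | Note | 60 | increased | 240 | – | end of Week 3 |

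The note's 240 mg/day after two active weeks is reproduced for the 80 mg/day start and not for the 60 mg/day start.

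**Cumulative prednisone for a 60 mg/day starter active at the first two checks.** Because the note does not name its first increase, I take Step 1 (80 mg) for Week 2 on both paths.

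- Uneventful taper from Step 2: 60×7 + 40×7 + (30 + 20 + 15 + 12.5 + 10 + 7.5 + 5 + 2.5)×14 = 420 + 280 + 1,435 = 2,135 mg over 18 weeks.
- Table, controlled at 120 mg in Week 3: 420 + 560 + 840 + 2,135 = 3,955 mg; 0 mg/day after 21 weeks.
- Note, controlled at 240 mg in Week 3 (Step B returns through Step A): 420 + 560 + 1,680 + 840 + 2,135 = 5,635 mg; 22 weeks.
- Table, controlled only at 240 mg in Week 4: 420 + 560 + 840 + 1,680 + 840 + 2,135 = 6,475 mg; 23 weeks.

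Note minus table is 5,635 − 3,955 = +1,680 mg (+42%) if 120 mg/day would have been enough, and 5,635 − 6,475 = −840 mg (−13%) if 240 mg/day was needed and worked. For a patient who fails on both paths, the dose up to failure is 420 + 560 + 1,680 = 2,660 mg (note) against 420 + 560 + 840 + 1,680 = 3,500 mg (table).

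**Sensitivity to the Week 2 assumption.** If the first increase under the note went to 120 mg, its total would be 420 + 840 + 1,680 + 840 + 2,135 = 5,915 mg, and the differences +1,960 mg (+50%) and −560 mg (−9%). The Week 3 conflict is unchanged.

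**Reach into the endpoints.**

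- *Taper length.* The target is stated as "Oral corticosteroids will be tapered to the target prednisone (or equivalent) dosage of 0 mg/day by Week 24". All three paths reach 0 mg/day at 21 to 23 weeks, before that target and before Week 36 (52 − 16), the latest start for 16 consecutive weeks. Taper length alone does not decide the primary endpoint.
- *Responder status.* It can differ only for a patient who is not controlled after a week at 240 mg/day in Week 3 but would have been controlled by the end of Week 4 on the table's path.
- *Visits.* The rows for "Flare assessment" and for prednisone dose in Protocol Appendix 1 show scheduled checks after Day 1 at Day 15 and Day 28, so failure at the end of Week 3 or Week 4 may first be recorded at the same visit.
- *Number affected.* The documents do not give it. As illustration only, if 25% to 75% start at 60 mg/day and 5% to 20% of those are active at both checks, 122×0.25×0.05 ≈ 2 to 122×0.75×0.20 ≈ 18 patients would face the conflict. Only a subset of these could change responder status.

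**The case against.** The best defence is that the note is a loose summary of the table and that neither binds the investigator. Table 1 gives recommendations, and Protocol Sections 3.3.4 and 4.4.1 leave increases up to 240 mg/day to the investigator's discretion, so either Week 3 dose is permitted. The failure criterion is defined by dose and duration, with no calendar date. The table alone already yields failure at Week 3 or Week 4 depending on the starting dose. The analyses use recorded doses and dates (SAP Section 4.7.2.1) and never refer to the note. The dose differences rest on an assumed Week 2 dose.

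Much of this stands, and it is why the point is minor. It does not remove the conflict. The note's reference to the schedule qualifies only the Day 1 starting dose; the 240 mg/day sentence sets its own dose and timing. Discretion to depart from a recommendation does not reconcile two different recommendations. Recorded doses carry any difference in site practice into the analysis.

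A further objection concerns time to sustained complete remission. SAP Section 4.7.2.3 censors treatment failures without remission at Week 52, but early withdrawals at withdrawal, and a failure before Week 12 involves both. I read the treatment-failure rule as the specific one, so the failure date does not matter there. If the withdrawal rule applied, the censoring date could differ between the two paths.

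**Conclusion.** The inconsistency is real and appears in both documents. For a 60 mg/day starter with activity at both of the first two weekly checks, Week 3 is 120 mg/day by the table and 240 mg/day by the note, and the earliest 240 mg/day failure moves by one week. Per affected patient, the cumulative dose under the note is 1,680 mg higher or 840 mg lower than under the table, given 80 mg/day in Week 2. The direction depends on the dose at which control would have come.

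Severity is minor. The rule is the same in both arms, the affected group is narrow and of unknown size, and there is no basis for claiming bias or loss of power. What is at stake is an avoidable doubling of the dose, and possibly a premature failure call, in individual patients.

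**What to change.** Let the step table govern. Limit the note's 240 mg/day clause to patients who start at 80 mg/day, and add one sentence: *Patients who started at 60 mg/day escalate to 80, then 120, then 240 mg/day after successive weeks with disease activity.* Make the same change in Protocol Table 1 and SAP Appendix 4, and tell sites by memo. The cost is one sentence in each document and the memo; data collection and analysis do not change.
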